#### **Complications**

Complications (i.e. any untoward medical event that occurs during the patient's illness/follow-up) will be reported and assigned a grade according to the Clavien-Dindo classification (slightly modified to allow for complications that are not post-operative in nature). The assigned grades will be reported descriptively by randomised group and overall and will also be used to generate a Comprehensive Complications Index (CCI) score for the 180 days following randomisation. The worst complication experienced (i.e. the complication with the highest grade assigned) during the 180 day follow-up period will be analysed using an ordinal regression model with fixed effects for allocation, the stratification factors and other relevant baseline covariates, and random intercepts for recruitment site. This model will be used to derive marginal effects (on both the risk ratio and risk difference scales) conditional on pre-specified representative values of the fixed effect covariates (e.g. Pr(Y > 1)Intervention, X)/Pr(Y > 1 | Control, X) for covariates X). Average marginal effects (on both the risk ratio and risk difference scales) will also be reported together with appropriate 95% confidence intervals for various relevant outcomes/cut-offs. The CCI will be analysed using a Gaussian family generalised linear mixed model, with an appropriate link function. This model will include fixed effects for allocation, the stratification factors and other relevant baseline covariates, and random intercepts for recruitment site. This model will be used to derive between group differences in expected CCI score with an appropriate 95% confidence interval and p-value.

## Relapse of cIAI

The proportion of patients that experience a relapse of cIAI during the 180 days following randomisation will be reported by randomised group. This outcome will be modelled using a mixed effect logistic regression model with fixed effects for allocation, the stratification factors and other prognostic baseline covariates, and random intercepts for study recruitment site. The estimated

conditional odds ratio for allocation, 95% confidence interval and p-value will be reported. To aid interpretability, point estimates and appropriate two-sided 95% confidence for the relative risk (cases/non-cases) and absolute risk reduction (based on the fitted model) will be reported, with the fixed effect covariates in the model set to various representative values (i.e. marginal risk ratios and risk differences at representative values). Average marginal effects on both the risk ratio and risk difference scales will also be reported with appropriate two-sided 95% confidence intervals.

#### Number of episodes of treatment failure

The total number of episodes of treatment failure during the 180 days following randomisation will be reported descriptively by randomised group and overall. For analysis, death within 180 days following randomisation will be coded as the "worst"/"highest" outcome (i.e. death will be ranked worse than any number of treatment failure episodes without death). This outcome and its empirical cumulative distribution function will be plotted by randomised group and overall. Total number of episodes of treatment failure (with death coded as the worst/highest outcome) will be compared using a proportional odds model, with fixed effects for allocation, the stratification factors and other prognostic baseline covariates, and random intercepts for study recruitment site. This model will be used to derive marginal effects (on both the risk ratio and risk difference scales) conditional on pre-specified values of interest for the fixed effects (on both the risk ratio and risk ratio and risk difference scales) will also be reported together with appropriate 95% confidence intervals for various relevant outcomes/cut-offs.

#### Re-admissions

The proportion of participants who are re-admitted to hospital during the 180 days following randomisation, and number of re-admissions per participant will be reported descriptively by randomised group and overall. The number of re-admissions per participant and empirical cumulative distribution function will also be plotted by randomised group and overall. The binary re-admission outcome (re-admitted vs not re-admitted during 180 days post-randomisation) will be modelled using a mixed effect logistic regression with fixed effects for allocation, the stratification factors and other prognostic baseline covariates, and random intercepts for study recruitment site. The estimated conditional odds ratio for allocation, 95% confidence interval and p-value will be reported. To aid interpretability, point estimates and appropriate two-sided 95% confidence intervals for the relative risk (cases/non-cases) and absolute risk reduction (based on the fitted model) will be reported, with the fixed effect covariates in the model set to various representative values (i.e. marginal risk ratios and risk differences at representative values). Average marginal effects on both the risk ratio and risk difference scales will also be reported with two-sided appropriate 95% confidence intervals. The count re-admission outcome (number of re-admissions during 180 days post-randomisation) will be analysed

using a proportional odds model, with fixed effects for allocation, the stratification factors and other prognostic baseline covariates, and random intercepts for study recruitment site. This model will be used to derive the difference in mean number of readmissions in each group, conditional on prespecified representative values of the fixed effect covariates, as well marginal effects (on both the risk ratio and risk difference scales) conditional on pre-specified representative values of the fixed effect covariates (e.g. Pr(Y > 0 | Intervention, X)/Pr(Y > 0 | Control, X) for covariates X). Average marginal effects (on both the risk ratio and risk difference scales) will also be reported together with appropriate 95% confidence intervals for various relevant outcomes/cut-offs.

#### All-cause mortality

Brief summaries of the total time at risk and number/proportion of participants who died will be presented by randomised group and overall. The number and proportion of participants who are lost to follow up or reach 180 days post-randomisation without experiencing an event, will be reported by group. Survival times will be illustrated using Kaplan-Meier cumulative incidence curves stratified by randomised group (without adjustment for any baseline covariates). Hazards will be compared using a proportional hazards model, with fixed effects for allocation and the stratification factors and shared frailties for recruitment site. The hazard ratio for allocation and appropriate two-sided 95% confidence interval and p-value will be reported. This model will be used to derive the estimated difference in median survival time, and an appropriate two-sided 95% confidence interval. A model including a treatment by time interaction will also be fitted to explore the presence and nature of any time-varying treatment effects.

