There are three published RCTs of antibiotic durations for cIAI; STOP-IT, DURAPOP and a cIAI feasibility trial [8, 12,13]. These trials all compared different antibiotic durations and together provide a signal of efficacy for longer antibiotic treatment durations. STOP-IT reported that a median of 4 days antibiotics was as effective as a median of 8 days, with surgical-site infection, recurrent intraabdominal infection, or death occurring in 21.8% as compared with 22.3% respectively (p=0.92). However, despite the limited difference in treatment durations, the longer antibiotic durations significantly delayed time until relapse (p=<0.001), which is consistent with an incompletely treated infection. DURAPOP assessed antibiotic durations for ICU patients with cIAI and compared 8 to 15 days of antibiotics. DURAPOPs secondary outcomes reported a significantly lower rate of radiological drainage in patients treated with 15 vs. 8 days antibiotics (9%, 11/116 vs. 19%, 23/120, p=0.04). Other outcomes signalled a 15-day treatment strategy may have benefits including: median length of ICU stay (12 days vs.13 day, p=0.14), rate of bacteraemia (4% vs.11%, p=0.059) and rate of microbiological failure (16% vs. 23%, p=0.13). The cIAI feasibility trial was a 30 patient RCT conducted in Leeds, UK, and designed after consultation with a Leeds Cancer-Patient and Public Involvement (LC-PPI) group [8]. It compared 28-days antibiotics to ≤10 days for patients with cIAI. It found a relapse rate of 4/17 (24%) in the ≤10-day arm, vs. 0/13 (0%) in the 28-day arm. Infections outside the abdominal cavity were diagnosed in 6/17 (35.3%) of those in the  $\leq 10$ -day arm, vs. 1/13(7.9%) in those treated for 28-days. Current UK practice and outcomes in patients with cIAI is described by a 417-patient observational study across 30 UK hospitals [5]. In the 17.3% of patients with relapse the median time until relapse was 18 days (IQR: 13-30 days); in the 11.3% of people who died the median time to death was 23 days (IQR: 12-51 days). Antibiotic treatment had a median duration of 12 days (IQR 7-18 days). The rate of adverse events in patients treated for cIAI varies by the patients group studied. Mortality rates have been reported at up to 50% in at risk populations with severe illness, and at 10 to 20% in studies from more broad populations of patients. The need for additional source control procedures, rate of relapses and rate of treatment failure likewise varies by population and definition, being reported in 20 to 60% of patients [2,3,15-19].

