#### 6.2 Exclusion criteria

• Perforated gastric ulcer or duodenal ulcer treated within 24 hours of the onset of symptoms

- Traumatic injury to the bowel (including iatrogenic or intra-operative) treated within 12 hours of injury
- Uncomplicated diverticulitis defined as an episode with a short history and with clinical signs of diverticulitis, with an increased body temperature and inflammatory parameters, verified by computed tomography (CT), and without any sign of complications such as abscess, free air or fistula.
- Grade 4 or 5 appendicitis defined by the 2017 American Association for the Surgery Trauma Grading System with either generalised peritonitis at surgery, or no or partial source control e.g. radiological drainage
- Non-perforated cholecystitis
- Ischemic or necrotic intestine without perforation
- Uterine perforation following uterine surgery treated within six hours of injury
- clAls with a low risk of complications who may receive more than 72 hours antibiotics are not intended to be included (such as those listed above: Traumatic injury to the bowel (including iatrogenic or intra-operative) treated within 12 hours of injury, Uterine perforation following uterine surgery treated within six hours of injury, Perforated gastric ulcer or duodenal ulcer treated within 24 hours of the onset of symptoms). Clinician assessment on the eligibility of patients receiving more than 72 hours of in-patient surgical care and antibiotics for their clAl may be required in patients who have clinically improved at this point and do not require active surgical care but remain in hospital and on antibiotics
- Current enrolment in another trial dictating antibiotic treatment duration
- Previous *Clostridium difficile* infection
- Infected necrotic pancreatitis
- Concomitant infection requiring ≥4 weeks antibiotic therapy including Intra-hepatic abscess/es
  planned to be treated with fixed-extended-duration antibiotics of 4 to 6 weeks antibiotics,
  osteomyelitis, and endocarditis
- Peritoneal dialysis
- Previously recruited for the EXTEND trial
- Treatment with Interleukin-6 Inhibitors
- High likelihood of death within 72 hours of randomisation in the opinion of the local Investigator
- Limitations in treatment decided before inclusion. Limitations in treatment that exclude patients from the EXTEND trial are those clinical decisions linked to an expectation the patient will die during this episode of infection.

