## 7.7 Long term follow-up assessments

No long-term follow-up beyond the initial 6-month follow-up period is planned.

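### The mortality analysis promises a difference in median survival, but neither arm's median is expected to be reached within the 180 days of follow-up

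*Protocol*

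**What the plan says.** Protocol section 10.2.4, All-cause mortality, specifies the model: "Hazards will be compared using a proportional hazards model, with fixed effects for allocation and the stratification factors and shared frailties for recruitment site". It reports a hazard ratio with interval and p-value, and then adds: "This model will be used to derive the estimated difference in median survival time, and an appropriate two-sided 95% confidence interval". The sentence carries no condition and offers no alternative if a median is not reached.

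The same text counts patients who "reach 180 days post-randomisation without experiencing an event", so survivors are censored at day 180. Section 7.7 confirms the horizon: "No long-term follow-up beyond the initial 6-month follow-up period is planned".

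On the level of mortality, section 1 reports from a 417-patient UK observational study that "in the 11.3% of people who died the median time to death was 23 days (IQR: 12-51 days". It puts mortality "at 10 to 20% in studies from more broad populations of patients", and it also says: "Mortality rates have been reported at up to 50% in at risk populations with severe illness". One exclusion in section 6.2 reads: "High likelihood of death within 72 hours of randomisation in the opinion of the local Investigator". No section states the mortality expected in the trial itself.

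**The concern.** A median survival time is the time at which the survival curve crosses 0.5. If the curve stays well above 0.5 up to the last day of observation, the data do not identify the median, the difference between two medians, or a confidence interval for that difference.

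The mortality figures quoted in the protocol point to that situation. What is at stake is the absolute effect on mortality. For binary outcomes, section 10.2.1 promises relative risks and absolute risk reductions with intervals. The All-cause mortality text instead names the median difference as its one model-based absolute contrast with an interval. If that cannot be produced, the section gives a relative effect with inference, but an absolute effect only descriptively.

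**Working it through.** **Inputs.** Horizon: 180 days (sections 7.7 and 10.2.4). Arm size: 583 (section 10.1). Mortality m by day 180: 11.3% and the range 10 to 20% (section 1), read as 180-day risks. That reading is an assumption, because section 1 gives no time horizon for these rates. Higher values are added to test how far the conclusion holds.

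**The plan's own figures.** The protocol gives no expected mortality or median, so there is none to reproduce. The arm size does reproduce: 524 per arm gives power 0.903 for 50% against 40% at two-sided 5%, and 524 / (1 − 0.10) = 582.2, rounded up to 583.

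**Step 1: is the median reached?** Survival at day 180 is S = 1 − m, and expected deaths per arm are 583 × m. The median is reached when at least 292 of 583 have died (292/583 = 0.501). The probability of that is an exact binomial tail, with every patient taken as followed to day 180.

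**Step 2: could a covariate pattern reach it?** Under proportional hazards, a patient whose hazard is h times that of a reference with mortality m has survival (1 − m)^h at day 180. Setting this to 0.5 gives h = ln 0.5 / ln(1 − m). At 11.3%, h = 0.693/0.120 = 5.8. At 20%, h = 0.693/0.223 = 3.1.

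**Step 3: what would extrapolation give?** With a constant hazard, the median is 180 × ln 2 / (−ln(1 − m)).

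| m | S at day 180 | Deaths per 583 | P(at least 292) | h needed | Exponential median (days) |
|---|---|---|---|---|---|
| 10% | 0.90 | 58 | 6e-132 | 6.6 | 1,184 |
| 11.3% | 0.887 | 66 | 3e-118 | 5.8 | 1,040 |
| 20% | 0.80 | 117 | 7e-59 | 3.1 | 559 |
| 40% | 0.60 | 233 | 5e-7 | 1.4 | 244 |
| 45% | 0.55 | 262 | 0.008 | 1.2 | 209 |
| 50% | 0.50 | 292 | 0.50 | 1.0 | 180 |

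**Step 4: how much does the assumed shape matter?** Take 11.3% as the 180-day risk and use the quoted quartiles of time to death. The cumulative risk is then 0.028 at day 12, 0.057 at day 23, 0.085 at day 51 and 0.113 at day 180.

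- A Weibull line through all four points, on the log cumulative-hazard against log time scale, has shape 0.50 and a median of about 4,500 days.
- A Weibull through days 23 and 180 only has shape 0.35 and a median of about 26,400 days.
- The exponential gives 1,040 days.

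The difference between arms is just as unstable. For an illustrative hazard ratio of 0.8 (not a protocol figure), the exponential median rises from 1,040 to 1,040/0.8 = 1,300 days, a difference of 260 days. The four-point Weibull median rises from about 4,502 to 4,502 × 0.8^(−1/0.501) = about 7,026 days, a difference of about 2,524 days. The same hazard ratio gives answers about ten times apart, because the assumed shape beyond day 180 determines the result.

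**The case against.** **A parametric model would give a number.** This is true, and the protocol does not say whether the proportional hazards model is Cox or parametric. It is therefore too strong to infer that the median does not exist. What stands is that it is not expected to be reached, and that any value returned depends on extrapolation well beyond 180 days.

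**Mortality may be higher.** Section 1 cites rates of up to 50%, and the trial recruits from intensive care. But that figure is for severely ill at-risk populations, while the trial also recruits from ordinary wards and excludes patients thought likely to die within 72 hours. Even at 45% an arm would reach its median with probability below 1%. A severely ill covariate pattern might have a predicted median inside 180 days, but the protocol names no such pattern for this outcome.

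**Absolute mortality is reported elsewhere.** A reader might infer that no absolute measure of mortality would remain. The documents do not support that. The mortality text itself gives deaths by group and Kaplan-Meier curves. The analyses of nights in hospital and of treatment-failure episodes rank death by day 180 as the top category and plan risk differences with intervals at various cut-offs. Those analyses do not name the death cut-off, however, and they work under a proportional odds constraint. The gap is confined to an adjusted contrast with an interval in the mortality section.

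**The SAP may deal with it.** A reader might also infer that a substitute would be picked after seeing the results. That is speculative: section 10.2.1 has the SAP approved during the pilot, before any outcome data are reviewed, so a replacement can still be pre-specified. The protocol has nevertheless fixed this quantity itself, so an SAP that follows it inherits the problem and one that departs from it contradicts it.

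**Conclusion.** The point holds in a limited form. Over the 10 to 20% mortality that the protocol cites, day-180 survival is 0.80 to 0.90 and each arm would see about 58 to 117 deaths, against about 292 needed. The median difference and its interval are not expected to be estimable within follow-up.

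This rests on reading the cited rates as 180-day risks in a population like the trial's. The conclusion is insensitive to that, and fails only if mortality in an arm approaches 50%.

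The consequence is modest. All-cause mortality is listed among the other secondary outcomes (section 3.5), and calling it the key safety outcome would go beyond the protocol. The hazard ratio, its interval and p-value, the time-interaction model, the curves and the descriptive proportions all remain valid. A Cox output of a median not reached would bias nothing. It would leave one promised result unreportable.

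**What to change.** In section 10.2.4, All-cause mortality, replace the sentence on the median difference with one that derives, from the same proportional hazards model, the standardised difference in 180-day survival probability between the arms with a two-sided 95% confidence interval. Standardised here means predicted survival under each allocation, averaged over the observed stratification factors, with a stated rule for handling the site frailty. This would also bring mortality into line with the absolute effects already planned for the binary outcomes.

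The difference in restricted mean survival time to day 180 is an optional addition or alternative. At 11.3% mortality and a constant hazard it would be about 170 days per arm, so it lies within the observed data.

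The cost is one sentence in the protocol and matching text in the SAP, with no extra patients, visits or data.

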### C. difficile infection

The proportion of patients that experience C. difficile infection during the 180 days following randomisation will be reported by randomised group. This outcome will be modelled using a mixed effect logistic regression model with fixed effects for allocation, the stratification factors and other prognostic baseline covariates, and random intercepts for study recruitment site. The estimated conditional odds ratio for allocation, 95% confidence interval and p-value will be reported. To aid interpretability, point estimates and appropriate two-sided 95% confidence intervals for the relative risk (cases/non-cases) and absolute risk reduction (based on the fitted model) will be reported, with the fixed effect covariates in the model set to various representative values (i.e. marginal risk ratios and risk differences at representative values). Average marginal effects on both the risk ratio and risk difference intervals.

#### Anti-microbial resistant infections

Participants will undergo passive surveillance for antimicrobial resistant infections (including MRSA, VRE, ESBL and CPE) during the 180 days following randomisation. The proportion of patients that experience each type of antimicrobial infection, number of days receiving carbapenem class antibiotics and the number of antibiotic class switches will be reported descriptively by randomised group and overall. Incidence of any antimicrobial resistant infection will be analysed using a mixed effect logistic regression model with fixed effects for allocation, the stratification factors and other prognostic baseline covariates, and random intercepts for study recruitment site. The estimated conditional odds ratio for allocation, 95% confidence interval and p-value will be reported. Point estimates and appropriate two-sided 95% confidence intervals for the relative risk (cases/non-cases) and absolute risk reduction (based on the fitted model) will be reported, with fixed effect covariates held at representative values. Average marginal effects on both the risk ratio and risk difference scales will also be reported with appropriate two-sided 95% confidence intervals. The number of days receiving carbapenem class antibiotics and the number of antibiotic class switches will be modelled using a proportional odds model, with fixed effects for allocation, the stratification factors and other prognostic baseline covariates, and random intercepts for study recruitment site. This model will be used to derive the difference in mean number of class switches and days receiving carbapenem. conditional on pre-specified representative values of the fixed effect covariates, as well marginal effects (on both the risk ratio and risk difference scales) conditional on pre-specified representative values of the fixed effect covariates (e.g. Pr(Y > 0 | Intervention, X)/Pr(Y > 0 | Control, X) for covariates X). Average marginal effects (on both the risk ratio and risk difference scales) will also be reported together with appropriate 95% confidence intervals for various relevant outcomes/cut-offs. Data on antimicrobial resistance will be used, in conjunction with antibiotic prescribing data, to assess the appropriateness of antibiotic therapy. Appropriateness will be assessed by a blinded clinician, and will be assigned as inappropriate, appropriate, or not determined.

